10.5. Appendix 5: Abbreviations

Term	Definition
AE	adverse event
AITC	allyl isothiocyanate
blinding/masking	A double-blind study is one in which neither the participant nor any of the investigator or sponsor staff who are involved in the treatment or clinical evaluation of the subjects are aware of the treatment received.
CKD-EPI	Chronic Kidney Disease Epidemiology Collaboration
CLBP	chronic low back pain
C_{max}	maximum serum/plasma concentration
complaint	A complaint is any written, electronic, or oral communication that alleges deficiencies related to the identity, quality, purity, durability, reliability, safety or effectiveness, or performance of a drug or drug delivery system.
compliance	Adherence to all study-related, good clinical practice, and applicable regulatory requirements
CRF	case report form
CV%	percent coefficient of variation
CYP3A	cytochrome P450 enzymes 3A
DDI	drug-drug interaction
data monitoring committee	A data monitoring committee is a group of independent scientists who are appointed to monitor the safety and scientific integrity of a human research intervention and to make recommendations to the sponsor regarding the stopping of a study for efficacy, or for harms, or for futility. The composition of the committee is dependent upon the scientific skills and knowledge required for monitoring the particular study.
DSA	disease-state appendix
ECG	electrocardiogram
eGFR	estimated glomerular filtration rate
enroll	The act of assigning a participant to a treatment. Participants who are enrolled in the study are those who have been assigned to a treatment.
IB	Investigator's Brochure
IC₅₀	half-maximal inhibitory concentration
IMP	Investigational Medicinal Product

informed consent	A process by which a participant voluntarily confirms his or her willingness to participate in a particular study, after having been informed of all aspects of the study that are relevant to the participant's decision to participate. Informed consent is documented by means of a written, signed, and dated informed consent form.
interim analysis	An interim analysis is an analysis of clinical study data, separated into treatment groups, that is conducted before the final reporting database is created/locked.
investigational product	A pharmaceutical form of an active ingredient or placebo being tested or used as a reference in a clinical trial, including products already on the market when used or assembled (formulated or packaged) in a way different from the authorized form, or marketed products used for an unauthorized indication, or marketed products used to gain further information about the authorized form.
ISA	intervention-specific appendix
NIMP	noninvestigational medicinal product
NOAEL	no-observed-adverse-effect level
NRS	Numeric Rating Scale
participant	Equivalent to CDISC term "subject": an individual who participates in a clinical trial, either as recipient of an investigational medicinal product or as a control
PK	pharmacokinetics
PO	by mouth
PoC	proof-of-concept
QD	once daily
QTc	corrected QT interval
SAD	single-ascending dose
SAE	serious adverse event
SAP	statistical analysis plan
screen	The act of determining if an individual meets minimum requirements to become part of a pool of potential candidates for participation in a clinical study.
SoA	Schedule of Activities
t_{1/2}	elimination half-life
TEAE	Treatment-emergent adverse event: An untoward medical occurrence that emerges during a defined treatment period, having been absent pretreatment, or worsens relative to the pretreatment state, and does not necessarily have to have a causal relationship with this treatment.
t_{max}	time to maximum plasma concentration

TRP	transient receptor potential
TRPA1	transient receptor potential ankyrin 1
WOCBP	women of childbearing potential

11. References

6.12.1. Extent of Exposure.....	11
6.12.2. Adverse Events	11
6.12.3. Deaths, Other Serious Adverse Events, and Other Adverse Events for Review	12
6.12.4. Clinical Laboratory Evaluation.....	12
6.12.5. Vital Signs and Other Physical Findings	13

- 6.12.6. Electrocardiograms13
- 6.12.7. Suicidal Ideation or Behavior13
- 6.13. Subgroup Analyses13
- 6.14. Protocol Deviations13
- 6.15. Interim Analyses and Data Monitoring14
- 6.16. Planned Exploratory Analyses14
- 6.17. Totality of Evidence for Safety14
- 6.18. Annual Report Analyses15
- 6.19. Clinical Trial Registry Analyses16
- 7. Unblinding Plan17
 - 7.1. PKPD Analysis Planning17
- 8. References18

3. Revision History

Statistical analysis plan (SAP) version 1 was approved on 17 December 2021 prior to unblinding data for H0P-MC-BP02 (BP02).

SAP version 2 was approved prior to unblinding data for Proof of Concept (PoC) lock. Major revisions included:

Section 6.1, the language describing active-treatment and post-active-treatment periods was made more clear.

Section 6.2, language was added to describe the derivation of PainDETECT total score.

Section 6.8, language was added to describe handling of specific edge cases when calculating treatment compliance.

Section 6.9, language describing reporting electronic Clinical Outcomes Assessment (eCOA) compliance separately for the active-treatment period was removed, since eCOA compliance is already reported on a weekly basis.

Section 6.10.1, language describing the derivation of nominal weeks for deriving the primary outcome was updated to handle a specific edge case observed in the H0P-MC-BP03 readout.

Section 6.12.7, a section on suicidal ideation and behavior was added to include language that it would be reported separately for the active-treatment period.

Section 6.13, a new subgroup variable was added for baseline PainDETECT total score.

Section 6.17, clarified the definition of Hy's Law and added a new endpoint under the Liver Function domain called DILI (drug-induced liver injury).

Section 7, added language that a CPMP-level blinding and unblinding plan now exists.

4. Study Objectives

4.1. Primary Objective

The primary objective of this intervention-specific appendix (ISA) is stated in the H0P-MC-CPMP (CPMP) protocol. Additional blinded details regarding LY3526318 dosing that are not included in the protocol can be found in the Ethics Review Board (ERB) supplement for Study BP02. For Study BP02, endpoint is defined as 4 weeks post initial treatment administration at Visit 5. Unless otherwise specified, the time point for secondary endpoint measurements is the same as that for the primary endpoint.

Objectives	Endpoints
Primary	
Efficacy of LY3526318 versus placebo in pain intensity	Mean change from baseline assessment to 4 weeks for average pain intensity as measured by the NRS

Abbreviation: NRS = Numeric Rating Scale.

4.2. Secondary Objectives

Secondary objectives applicable to all ISAs are listed in the CPMP SAP version 5.

Additional secondary endpoints specific to Study BP02 are listed below.

Objective	Endpoint Measure
Other Secondary	
Physical Functioning Efficacy of LY3526318 versus placebo	
 Mean change from baseline to endpoint in RMDQ total score Proportion of participants with reduction from baseline of at least 3.5 points in RMDQ total score at each time point Proportion of participants with reduction from baseline greater than or equal to 30%, 50%, and 70% in RMDQ total score at each time point Time to first treatment response with at least 30%, 50%, and 70% reduction from baseline in RMDQ total score

Abbreviation: RMDQ = Roland-Morris Disability Questionnaire.

4.3. Exploratory Objectives

The following exploratory objectives and endpoints are specific to Study BP02.

Objectives	Endpoints
Tertiary/Exploratory	
Measure the pharmacokinetics of LY3526318 in participants with CLBP.	Measure of plasma concentrations of LY3526318 to enable PK evaluations
(Duration of response) Efficacy of LY3526318 versus placebo	Mean change from baseline assessment up to 8 weeks for average pain intensity as measured by the NRS

Abbreviations: CLBP = chronic low back pain; NRS = numeric rating scale; PK = pharmacokinetic.

5. Study Design

5.1. Summary of Study Design

The CPMP protocol provides a summary of the overall study design for the chronic pain master protocol. ISA-specific study design is provided in the BP02 protocol.

In this ISA, patients in the LY3526318 treatment arm receive LY3526318 for the first 4 weeks of the double-blind period (active-treatment period) and switch to placebo for the last 4 weeks of the double-blind period (post-active-treatment period) starting on the day of Visit 5. Placebo patients receive placebo for the entire 8-week, double-blind period. Additional details of the study design may be found in the ERB supplement for Study BP02.

For the analyses listed in this SAP, except for treatment compliance, we define the active-treatment period and post-active treatment period as follows. The first 4 weeks of the double-blind period (active-treatment period) ends at the day of Visit 5. The last 4 weeks of the double-blind period (post-active-treatment period) begins the day after Visit 5.

5.2. Determination of Sample Size

Approximately 150 participants will be randomized in a CCI ratio to LY3526318 and placebo, respectively. It is expected that approximately 85% of participants will complete the double-blind treatment period of the study CCI

CCI

If there is no treatment difference between placebo and LY3526318, the probability of passing the efficacy criterion specified above (that is, false positive) is less than 0.05. The simulation for the power calculation and sample size determination was carried out in Fixed and Adaptive Clinical Trial Simulator (FACTS) version 6.0.

5.3. Method of Assignment to Treatment

The method of treatment assignment is described in the CPMP SAP version 5.

6. A Priori Statistical Methods

6.1. General Considerations

The estimand for the primary clinical question of interest has been described in the CPMP SAP version 5.

Unless otherwise specified, efficacy analyses will be conducted for the first 4 weeks of the double-blind period (active-treatment phase) and separately for the entire 8-week study. A post-active-treatment population will be used for analyses of the last 4 weeks of the double-blind period (post-active-treatment phase) and will include all patients who do not discontinue at or prior to Visit 5. For treatment-emergent adverse events (TEAEs), participants in the post-active-treatment population will be analyzed according to the treatment they receive during the active-treatment phase. Adverse event (AE) analyses will be reported for the first 4 weeks of the double-blind period (active-treatment phase) and separately for the last 4 weeks of the double-blind period (post-active-treatment phase). Some AEs may be reported for the entire 8 weeks if necessary. Laboratory, electrocardiogram (ECG), and vital sign results will be reported for the active-treatment phase and separately for the entire 8-week study.

Other general considerations for analyses are described in the CPMP SAP version 5.

6.2. Adjustments for Covariates

The general adjustment strategy has been described in the CPMP SAP version 5.

Randomization into Study BP02 is stratified by the presence of neuropathic pain as defined by the painDETECT score. The following stratification factor will be included in the models for the primary, secondary, and some exploratory outcomes.

Neuropathic pain	painDETECT score
Positive presence	≥ 19
Unclear or negative	< 19

The painDETECT total score is derived from patient responses to 9 questions on the painDETECT questionnaire. Seven questions ask about the gradation of pain, scored from 0 to 5 (never = 0, hardly noticed = 1, slightly = 2; moderately = 3, strongly = 4, very strongly = 5). One question asks about the pain course pattern, scored from -1 to 2, depending on which pain course pattern diagram is selected. Another question asks about radiating pain, answered as yes or no and scored as 2 or 0, respectively. The final score is between -1 and 38, and a score of 19 or higher suggests that pain is likely to have a neuropathic component (Freyhagen et al. 2006).

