6.7. Participant Characteristics

The summary of participant characteristics has been described in the CPMP SAP version 5.

ISA-specific considerations are described below:

painDETECT ≥ 19 (that is, positive for neuropathic pain)

Roland-Morris Disability Questionnaire (RMDQ) total score at baseline.

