6.10.3. Secondary Efficacy Analyses

Secondary efficacy analyses common to all ISAs within CPMP have been described in the CPMP SAP version 5. Unless otherwise specified, the time point for secondary endpoint measurements is the same as that for the primary endpoint. Study BP02 will also consider the following secondary analyses.

The RMDQ is a simple, sensitive, and reliable method to measure disability in patients with back pain. The RMDQ consists of 24 statements relating to the person's perceptions of back pain and associated disability based on:

- physical ability/activity
- sleep/rest
- psychosocial
- household management
- eating, and
- pain frequency.

Participants are asked if they feel the statement is descriptive of their own circumstance on that day. The total score is obtained by counting the number of “Yes” responses, ranging from 0 = no disability to 24 = maximal disability.

A Bayesian longitudinal mixed-effect model repeated measures (MMRM) analysis will be performed to evaluate the change from baseline to each postbaseline visit in the RMDQ total score. The model will utilize the constrained cell means model so that a common mean is estimated at baseline. More details on this approach are provided in the CPMP SAP version 5.

This table describes information included in the model.

Categorical effects	the interaction of treatment and time point (constrained to estimate a common mean at baseline across treatments) average baseline pain severity category (baseline NRS < 7, baseline NRS ≥ 7) presence of neuropathic pain (painDETECT ≥ 19, painDETECT < 19) pooled investigative site
Continuous covariates	none

Abbreviation: NRS = numeric rating scale.

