6.13. Subgroup Analyses

General subgroup analyses are described in the CPMP SAP version 5.

Study BP02 will also consider the following subgroup analyses for the primary outcome.

Subgroup Variable	Categories
Neuropathic pain	Categories: Positive presence (painDETECT total score ≥19), Unclear or negative (painDETECT total score <19)

The subgroup analyses will be conducted using similar modeling approaches as the primary analysis. Additional factors in the model are described in the CPMP SAP version 5. The treatment difference at the endpoint will be reported within each level of the subgroup factor along with 95% credible intervals. Frequentist MMRM may be performed as a sensitivity analysis using the modeling approach described in the CPMP SAP version 5.

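### SAP 6.2's painDETECT item scores sum to a maximum of 39, but the same paragraph gives the maximum as 38

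*SAP*

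**What the plan says.** SAP 6.2 (Adjustments for Covariates) defines the painDETECT total as the sum over nine questions and gives the score for each type:

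- Gradation of pain: "Seven questions ask about the gradation of pain, scored from 0 to 5".
- Pain course: "One question asks about the pain course pattern, scored from -1 to 2, depending on which pain course pattern diagram is selected".
- Radiating pain: "answered as yes or no and scored as 2 or 0, respectively".

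It then gives the range of the total: "The final score is between -1 and 38". A total of 19 or more is read as a likely neuropathic component.

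According to the SAP's Revision History, this paragraph was new in version 2: "language was added to describe the derivation of PainDETECT total score". The same version added the painDETECT subgroup.

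The total, cut at 19, is used in several places:

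- SAP 6.2 names it as a randomisation stratification factor and puts it in the primary, secondary and some exploratory models.
- SAP 6.7 reports it as a baseline characteristic ("that is, positive for neuropathic pain").
- SAP 6.9 adds painDETECT as a covariate in the rescue-medication model.
- SAP 6.10.3 includes the two-level factor in the model for the Roland-Morris total.
- SAP 6.13 defines a subgroup for the primary outcome by it: "Positive presence (painDETECT total score ≥19".

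**The concern.** The paragraph exists to tell a programmer how to compute the total, and its parts do not agree. The item scores allow a total of 39, while the stated maximum is 38. No cap or rescaling that would reconcile them appears in either document.

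What is at stake depends on which figure is wrong. An error in the stated maximum alone has no consequence, because the total and the cut at 19 do not depend on it. If an item score is one point too high and the total is derived as written, everyone who gave that response gains a point. Those whose correct total is 18 then cross the cutoff, always upwards. This would reach any flag derived from the text: chiefly the subgroup in SAP 6.13 and the baseline row in SAP 6.7. The model covariate would be affected only if it is re-derived from item data rather than taken from the randomisation record.

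**Working it through.** **1. Range from the item scores in SAP 6.2**

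| Item | Number | Minimum | Maximum |
|---|---|---|---|
| Gradation | 7 | 7 × 0 = 0 | 7 × 5 = 35 |
| Pain course | 1 | -1 | 2 |
| Radiating pain | 1 | 0 | 2 |
| **Total** | **9** | **-1** | **39** |

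The item count and the minimum match the text. The maximum does not: 39 against 38.

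**2. What would give 38**

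- Pain-course maximum 1: 35 + 1 + 2 = 38.
- Radiating-pain score 1: 35 + 2 + 1 = 38.
- Both lowered: 35 + 1 + 1 = 37.
- Six gradation items: 30 + 2 + 2 = 34. Eight: 40 + 2 + 2 = 44.

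The candidates are therefore the pain-course maximum, the radiating-pain score, or the stated 38 itself.

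**3. Who would change category if an item score is wrong**

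Only a participant with a correct total of 18 and a written total of 19.

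- Pain-course error: top-scored diagram chosen, and a gradation sum of 17 without radiating pain (17 + 2 + 0 = 19 as written, 18 correct) or 15 with it (15 + 2 + 2 = 19 as written, 18 correct).
- Radiating-pain error: answer is yes, and gradation sum plus pain-course score equals 17 (17 + 2 = 19 as written, 17 + 1 = 18 correct).

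**4. How many of 150**

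The documents give no score distribution, so these inputs are assumptions: totals roughly normal with mean 12 to 18 and SD 6 to 8; 20% to 60% choose the top-scored diagram; 30% to 70% answer yes to radiating pain.

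P(correct total = 18) = Φ((18.5 − mean)/SD) − Φ((17.5 − mean)/SD)

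- Lowest (mean 12, SD 8): Φ(0.8125) − Φ(0.6875) = 0.0376.
- Highest (mean 18, SD 6): Φ(0.0833) − Φ(−0.0833) = 0.0664.
- Mid case (mean 15, SD 7): Φ(0.5000) − Φ(0.3571) = 0.052.

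Ceiling, whatever the link between item response and total: 150 × 0.0376 = 5.6 to 150 × 0.0664 = 10.0.

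If the response is independent of the correct total:

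- Pain-course maximum too high: 150 × 0.2 × 0.0376 = 1.1 to 150 × 0.6 × 0.0664 = 6.0.
- Radiating-pain score too high: 150 × 0.3 × 0.0376 = 1.7 to 150 × 0.7 × 0.0664 = 7.0.
- Mid case, 40% choosing the top diagram: 150 × 0.4 × 0.052 = 3.1.
- Only the stated maximum wrong: 0.

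**5. Independence**

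An item-level simulation let the affected response correlate with the rest of the score (inter-item latent correlation 0.3 to 0.5; loading of the affected item 0 to 0.6). It gave 1.0 to 5.4 of 150 for the pain-course case and 1.4 to 6.1 for the radiating-pain case. Its totals had mean 10.8 to 17.2 and SD 5.8 to 8.3, which overlaps the ranges in step 4 without matching them, so it is a rough check only.

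**The case against.** The strongest reply is that this may be a one-digit slip in a descriptive sentence. Any consequence needs two things that the documents do not establish: that an item score rather than the 38 is wrong, and that the program follows this text rather than the instrument's own key. The reach is also limited. SAP 5.3 leaves treatment assignment to the master protocol's SAP, and Protocol 6.3 adds no stratification factor for this appendix, so the scoring actually used at randomisation may sit in documents not available here. A covariate taken from the randomisation record would be untouched. The participant counts rest entirely on assumed distributions.

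Most of this stands. Nothing in the documents shows that the wording was used to assign strata or that anyone has been misclassified, and the counts are illustrations of scale. The contradiction itself is not answered. The paragraph is current, unbroken and unredacted text, it was added to specify this derivation, and it is the only item scoring the two documents give. That programmers will use the key instead is plausible, but the plan does not say so.

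**Conclusion.** The contradiction is certain: the items as written give -1 to 39, and the paragraph says -1 to 38. Confidence is high on that and does not extend to any misclassification having occurred.

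The effect is zero if only the stated maximum is wrong. If an item score is one point too high and is programmed as written, roughly 1 to 7 of 150 participants would move into the ≥19 group under the assumed distributions and independence, about 3 in the mid case. Without independence the number cannot exceed those with a correct total of 18, which is 5.6 to 10.0 under the same distributions.

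The score is a baseline measure and the text sets the same scoring for both arms, so the effect on the overall treatment estimate would be small. The exposed results are the neuropathic-pain subgroup and the baseline summary. Severity is minor.

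**What to change.** Compare the item scores and the range in SAP 6.2 with the instrument's scoring key and correct whichever figure is wrong. Before database lock, confirm that the program deriving the ≥19 flag uses that key. The cost is a one-line SAP correction and one check of the derivation program; the design and the cutoff of 19 stay as they are.

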6.3. Handling of Dropouts or Missing Data

The missing data strategy has been described in the CPMP SAP version 5.

6.4. Multiple Comparisons/Multiplicity

There is no plan to formally adjust for multiplicity.

6.5. Use of an “Efficacy Subset” of Participants

There are no plans to use a modified efficacy subset.

6.6. Participant Disposition

The summary of participant disposition has been described in the CPMP SAP version 5. Disposition will additionally be reported for the first 4-week, active-treatment period.

6.7. Participant Characteristics

The summary of participant characteristics has been described in the CPMP SAP version 5.

ISA-specific considerations are described below:

painDETECT ≥ 19 (that is, positive for neuropathic pain)

Roland-Morris Disability Questionnaire (RMDQ) total score at baseline.

6.8. Treatment Compliance

Treatment percentage of compliance will be calculated as:

$$\frac{\text{Total pills taken} * 100}{\text{Total pills expected}}$$

with total pills taken calculated by total pills dispensed minus total pills returned. A patient is considered to be compliant for a given period if this percentage is between 80% and 120%. Treatment compliance will be reported for the first 4 weeks of the study period (Visit 3 to 5, not including the day of Visit 5) and separately for the last 4 weeks of the study period (Visit 5 to 7, including the day of Visit 5). Note that if a participant misses returning pills at Visit 4 or Visit 5, there will be an issue calculating compliance for the active-treatment period, and alternate methods for calculating compliance may be considered. For participants who discontinue early, time after the penultimate visit will be excluded for calculation of treatment compliance. For example, if a participant discontinued early at Visit 6, treatment compliance will be derived only from data collected through Visit 5. Comparisons between treatment group for treatment compliance will be performed using a Fisher’s exact test. Listings for treatment compliance of individual patients by treatment period will also be provided.

Depending on the level of observed treatment compliance, and where appropriate, sensitivity analyses of primary and key secondaries may be conducted by excluding patients with poor treatment compliance.

